12. After you have treated both your right and left ears for a total treatment time of 10 minutes, the treatment session is complete, and you may remove the safety googles.

PROCEDURE ADMINISTRATION PHASE MEASURES

DAILY TREATMENT ADMINISTRATION LOG

The study site will provide the subject data capture forms to record each day when they have administered a treatment with the Erchonia® THL ™ Laser. The subject will provide the study investigator the completed "Treatment administration log" following the 4-week treatment procedure administration phase.

WEEKLY ASSESSMENTS

Once a week, the site staff may call and/or contact the subject by e-mail to check on compliance, to verify that no adverse events had occurred, and to answer any questions the subject may have.

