4 WEEK EVALUATION: TREATMENT END

Following completion of the entire 4 weeks of study procedure administrations with the Erchonia® THL [™], the following will be recorded by the site investigator as outlined in the STUDY TEST BATTERY section above.

- Tinnitus Functional Index (TFI)
- Audiometric Test: Degree of Hearing Loss
- > Tympanometry
- Otoscopic Examination of the Ears
- Subject Satisfaction With Study Outcome
- Subject Perceived Group Allocation and Rationale

POST-PROCEDURE ACTIVITIES

2 Weeks Post-Procedure: STUDY ENDPOINT

Two weeks following the completion of the 4-week treatment administration phase, the following will be recorded by the site investigator) as outlined in the STUDY TEST BATTERY section above. These recordings will form the study endpoint data set from which change from baseline will be evaluated with respect to assessing study outcome.

- Tinnitus Functional Index (TFI)
- Audiometric Test: Degree of Hearing Loss
- > Tympanometry
- Otoscopic Examination of the Ears
- Subject Satisfaction With Study Outcome
- > Subject Perceived Group Allocation and Rationale

ADVERSE EVENTS

The subject will be instructed to notify the PI any time that a potential adverse event has been experienced. It is unlikely and not expected that any adverse events will result from implementation of this clinical study protocol. Prior clinical trials using low level laser light have not typically yielded any adverse events or reactions. However, potential adverse events that may feasibly occur from application of the Erchonia® THL[™] include, but are not necessarily limited to skin irritation, discoloring, rash, indentations, and infection.

PRIVACY AND CONFIDENTIALITY

Records for each subject in this clinical study will be maintained in separate files in a locked filing cabinet at the respective test site. The investigator at the test site will be responsible for ensuring that all records for a subject pertaining to his or her participation in the clinical study are stored in that subject's file at all times other than when information is being recorded on them.

Copies of all of the subject case report forms will be made and supplied to Regulatory Insight, Inc. and Erchonia Corporation. Regulatory Insight, Inc. and Erchonia Corporation will maintain these copies in a separate clinical study file that is kept in a locked filing cabinet at their respective premises. The original records will be maintained at the respective test sites.

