Statistical evaluation of blinding efficacy will be performed as follows:

- (i) The percentage of subjects who correctly perceived their procedure group assignment and the percentage of subjects who did not correctly perceive their procedure group assignment will be calculated.
- (ii) The Fischer's Exact categorical analysis technique for comparison of proportion of successes (accurate procedure group assignment determination) and failures (inaccurate procedure group assignment determination) between subject groups will be performed for each of the subject.
- (iii) **Qualitative analysis confirmation:** Evaluation of the comments provided by the subject in the rationale section to explain the guess at group assignment will be evaluated and interpreted as follows to either support or negate the numerical findings:
 - Positive blinding efficacy will be supported through qualitative assessment of comments provided to support perceived group assignment that pertain to the determination being based on treatment efficacy or lack thereof, e.g.: 'I barely notice my tinnitus anymore, so I believe I got the real treatment' or 'I haven't noticed any change in my tinnitus, so I believe I got the fake treatment.'
 - Blinding will be determined to have failed if comments provided to support perceived group assignment pertain to factors such as sensation/visual clues, such as 'I saw/didn't see a light go on'.

SAFETY ANALYSES

Safety analyses will be based on all subjects who were randomized to the test or to the placebo procedure group. Safety will be assessed by evaluating and comparing frequency and incidence of observed and/or reported adverse events between test and placebo procedure groups. A chisquare test with a continuity correction will be performed to compare the percentage of subjects who had adverse events between test and placebo group subjects.

Additionally, safety will be assessed through tracking of the following across study duration:

- a. changes in audiometric evaluations, including PTAs.
- b. Changes in tympanogram type.
- c. Changes in otoscopic evaluation findings.

INFORMED CONSENT

- Informed consent will be an agreement between the individual investigator and each subject, having the capacity to understand and make an informed decision. Consent will be obtained prior to each potential subject's participation in this clinical study.

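### No required, scheduled adverse-event inquiry is specified, so the between-group adverse-event comparison depends largely on subject-initiated reports

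*Combined protocol and SAP*

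**What the plan says.** All references are to the combined protocol and SAP.

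- **Weekly Assessments** (under Procedure Administration Phase Measures): once a week during treatment, "the site staff may call and/or contact the subject by e-mail to check on compliance, to verify that no adverse events had occurred". No minimum number of contacts and no standard question is given.
- **Daily Treatment Administration Log**: subjects receive "data capture forms to record each day when they have administered a treatment". No field for symptoms or events is described.
- **Adverse Events**: "The subject will be instructed to notify the PI any time that a potential adverse event has been experienced". The events the plan foresees include "skin irritation, discoloring, rash, indentations, and infection".
- **4 Week Evaluation** and **2 Weeks Post-Procedure** (study endpoint): each lists the same six items, namely the TFI, audiometry, tympanometry, otoscopy, satisfaction and perceived allocation.
- **Safety Analyses**: in all randomized subjects, safety is assessed by "evaluating and comparing frequency and incidence of observed and/or reported adverse events between test and placebo procedure groups". The percentage of subjects with events is compared by a chi-square test with continuity correction. Changes in audiometry, tympanogram type and otoscopic findings are also tracked.

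**The concern.** A test of event percentages counts every subject without a recorded event as event-free. That is sound only if subjects were asked, and asked in the same way. Here the one contact that mentions adverse events is optional, while neighbouring duties, such as supplying the log and recording the visit assessments, are written with *will*.

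The treatment is 28 self-administered sessions at home, out of sight of site staff. A mild or passing event reaches the data only if the subject thinks it worth reporting or a staff member happens to ask. If few events are recorded, the reader cannot tell whether few occurred or few were volunteered. For a device meant for prescription home use, that is the safety question that matters.

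**Working it through.** **1. Each route by which an event could be recorded**

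| Route | Required as written? | Would it bring out an event? |
|---|---|---|
| Weekly call or e-mail, treatment weeks only | No (*may*) | Yes, if made |
| Daily log | Yes | None described; it records treatment days |
| Week-4 visit list | Yes | Ear and hearing findings; no event question |
| Contact between treatment end and endpoint visit | None described | – |
| Study-endpoint visit list | Yes | Ear and hearing findings; no event question |
| Subject notifies the investigator | Instruction to the subject | Only if the subject volunteers it |

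No row is both required of the site and an inquiry about events. A subject who stops early and misses the week-4 visit stays in the safety population with no required inquiry at all.

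**2. Do the scheduled examinations fill the gap?** The otoscopy section records the ear canal, the eardrum and the position of the malleus. The administration instructions sweep the laser from above the ear down the side of the neck, and the anticipated events are mainly on the skin. A rash on the neck or outer ear is not an otoscopy item, and a short-lived one could clear before week 4. The examinations fill the gap only in part.

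**3. Size: illustration only.** The plan states no event rate, expected event count or safety power, so there is no safety figure to reproduce. The group size of 32 comes from the Sample Size Determination section: 29 / (1 − 0.083) = 31.62, rounded up to 32. Event rates *p* and capture fractions *c* (the share of affected subjects whose event is recorded) are assumptions.

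*Chance that no subject among 32 has a recorded event* = (1 − *p* × *c*)^32:

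| Assumed *p* | *c* = 1 | 0.8 | 0.6 | 0.5 | 0.4 |
|---|---|---|---|---|---|
| 5% | 0.194 | 0.271 | 0.377 | 0.445 | 0.524 |
| 10% | 0.034 | 0.069 | 0.138 | 0.194 | 0.271 |

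For example, with *p* = 0.10 and *c* = 0.5, (1 − 0.05)^32 = 0.194.

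*Power of the planned continuity-corrected chi-square test*, by exact binomial enumeration with 32 per group and equal capture in both groups. The 0.05 level is assumed, because Safety Analyses states none:

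| Assumed true rates, placebo vs test | *c* = 1 | 0.8 | 0.6 | 0.5 | 0.4 |
|---|---|---|---|---|---|
| 5% vs 15% | 0.110 | 0.063 | 0.026 | 0.014 | 0.006 |
| 5% vs 25% | 0.484 | 0.327 | 0.174 | 0.107 | 0.054 |
| 10% vs 30% | 0.403 | 0.286 | 0.165 | 0.110 | 0.063 |

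Equal under-capture shrinks the difference in proportion. At 5% vs 25% and *c* = 0.5, the 20-point true difference appears as 0.5 × 20 = 10 points. Expected affected subjects fall from 1.6 vs 8.0 to 0.8 vs 4.0.

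**The case against.** The strongest reply has four parts.

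- **The plan does foresee asking.** A weekly contact with adverse events as a stated purpose is written in, and sites may make every one. This stands: a reader might infer that events are never asked about on a schedule, and the documents do not support that. What is missing is the obligation.
- **Safety does not rest on volunteered reports alone.** Observed events count too, and audiometry, tympanometry and otoscopy are required at both later visits. This also stands, within the limits shown in step 2.
- **Silence in a visit list is weak evidence.** The lists name tools from the test battery, not every visit procedure. The completed treatment log, handed over after the treatment phase, is not on the week-4 list either. The case report forms (Appendix N) may hold an adverse-event page, and the monitoring plan was also not available. This limits the claim to the text at hand. A form page would still not make the weekly contact mandatory, although it could prompt an inquiry at the visits.
- **Blinding protects the comparison.** Subjects and site staff do not know the allocation. A reader might infer that optional contact biases one group against the other; nothing in the documents shows this. Blinding limits differential capture, but equal under-capture still hides events and shrinks a true difference.

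The low power at full capture is also a fair point: group size limits this test however events are collected.

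**Conclusion.** The concern holds in a limited form. The available text specifies no mandatory scheduled adverse-event inquiry at any point from the first home session to the study endpoint. The between-group comparison therefore depends largely on subject-initiated reports and risks under-counting, with the ear and hearing examinations a partial safeguard.

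It would go too far to say that events will be under-counted, or that a low rate would merely reflect not asking. Actual capture is unknown and could be high. The figures show how much capture could matter under assumed rates; they do not predict this trial. Efficacy endpoints, sample size and alpha are unaffected. The change is worth making because it is cheap and makes a low event count interpretable.

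**What to change.** 1. In Weekly Assessments, change *may* to *will*, so that every subject is contacted once in each of the 4 treatment weeks.
2. At each contact ask every subject the same neutral open question, for example whether any new or changed symptom or problem has been noticed since the last contact. This replaces a purpose worded as verifying that nothing occurred.
3. Add that question to the week-4 and study-endpoint lists, recorded before the perceived-allocation item so that the guess cannot colour the answer. The endpoint question should cover the 2 weeks since treatment ended.
4. Confirm that the case report forms carry the item, including a recorded *none*, and mark whether each event was solicited or spontaneous.

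Cost: at most 4 × 64 = 256 short calls or e-mails by existing staff, and one form line per visit. The downside is that more minor events will be recorded. The change will not make the safety test well powered.

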4 WEEK EVALUATION: TREATMENT END

Following completion of the entire 4 weeks of study procedure administrations with the Erchonia® THL [™], the following will be recorded by the site investigator as outlined in the STUDY TEST BATTERY section above.

- Tinnitus Functional Index (TFI)
- Audiometric Test: Degree of Hearing Loss
- > Tympanometry
- Otoscopic Examination of the Ears
- Subject Satisfaction With Study Outcome
- Subject Perceived Group Allocation and Rationale

POST-PROCEDURE ACTIVITIES

2 Weeks Post-Procedure: STUDY ENDPOINT

Two weeks following the completion of the 4-week treatment administration phase, the following will be recorded by the site investigator) as outlined in the STUDY TEST BATTERY section above. These recordings will form the study endpoint data set from which change from baseline will be evaluated with respect to assessing study outcome.

- Tinnitus Functional Index (TFI)
- Audiometric Test: Degree of Hearing Loss
- > Tympanometry
- Otoscopic Examination of the Ears
- Subject Satisfaction With Study Outcome
- > Subject Perceived Group Allocation and Rationale

ADVERSE EVENTS

The subject will be instructed to notify the PI any time that a potential adverse event has been experienced. It is unlikely and not expected that any adverse events will result from implementation of this clinical study protocol. Prior clinical trials using low level laser light have not typically yielded any adverse events or reactions. However, potential adverse events that may feasibly occur from application of the Erchonia® THL[™] include, but are not necessarily limited to skin irritation, discoloring, rash, indentations, and infection.

PRIVACY AND CONFIDENTIALITY

Records for each subject in this clinical study will be maintained in separate files in a locked filing cabinet at the respective test site. The investigator at the test site will be responsible for ensuring that all records for a subject pertaining to his or her participation in the clinical study are stored in that subject's file at all times other than when information is being recorded on them.

Copies of all of the subject case report forms will be made and supplied to Regulatory Insight, Inc. and Erchonia Corporation. Regulatory Insight, Inc. and Erchonia Corporation will maintain these copies in a separate clinical study file that is kept in a locked filing cabinet at their respective premises. The original records will be maintained at the respective test sites.

Subjects' identities will be kept confidential by assigning each subject a unique de-identified subject ID upon acceptance into the study. The subject ID will comprise the investigator's two initials (first and last name initials) and a three-digit number that will be based upon the subject's order of entry into the clinical study. For example, under Study Investigator John Black, the third subject enrolled in the study would have a subject ID of JB003.

MONITORING OF THE CLINICAL STUDY

A Clinical Trial Monitoring Plan will be in place to ensure on-going compliance and accuracy of procedures throughout the trial.

STATISTICAL ANALYSIS

BASELINE VARIABLES EVALUATION

A. Tinnitus Variables

Baseline tinnitus variables of tinnitus etiology, and time since tinnitus onset will be summarized descriptively (mean and standard deviation, and categorically, as applicable) and compared for differences between procedure groups and test sites, as applicable. Any identified differences will be explored with respect to impact on study outcome.

B. Medication and Treatment

Subjects' prior treatment approaches for tinnitus reduction and baseline concomitant medication and therapy use will be summarized categorically and compared for differences between procedure groups and test sites. Any identified differences will be explored with respect to impact on study outcome.

C. Hearing Aid Use

Subjects' use of hearing aids will be summarized descriptively. Any identified differences will be explored with respect to impact on study outcome.

D. Subject Demographics:

Demographics of age, gender and ethnicity will be summarized descriptively (mean and standard deviation, and categorically, as applicable) and compared for differences between procedure groups and test sites. Any identified differences will be explored with respect to impact on study outcome.

PRIMARY EFFICACY OUTCOME MEASURE: CHANGE IN TOTAL SCORE ON THE TINNITUS FUNCTIONAL INDEX(TFI) FROM BASELINE TO STUDY ENDPOINT

Primary efficacy outcome measure for this clinical study is a statistically significant difference in the proportion of subjects between test and control groups who achieve a clinically meaningful decrease in total score on the TFI from baseline to study endpoint.

The TFI has been highly recommended to be used in both clinical and research settings for tinnitus measurement because of its responsiveness to treatment-related change, validity for scaling the overall severity of tinnitus, and comprehensive coverage of multiple domains of tinnitus severity (Meikle et al., 2011).

The following abstract pertains to a reference study that served to establish the industry-standard minimal clinically relevant difference of change in TFI total score from pre- to post-intervention as 13 points. This reference has been cited and supported through numerous subsequent prospective and retrospective trials and analyses and is considered industry-wide.

Objectives: Chronic subjective tinnitus is a prevalent condition that causes significant distress to millions of Americans. Effective tinnitus treatments are urgently needed but evaluating them is hampered by the lack of standardized measures that are validated for both intake assessment and evaluation of treatment outcomes. This work was designed to develop a new self-report questionnaire, the Tinnitus Functional Index (TFI), that would have documented validity both for scaling the severity and negative impact of tinnitus for use in intake assessment and for measuring treatment-related changes in tinnitus (responsiveness) and that would provide comprehensive coverage of multiple tinnitus severity domains.

Design: To use preexisting knowledge concerning tinnitus-related problems, an Item Selection Panel (17 expert judges) surveyed the content (175 items) of nine widely used tinnitus questionnaires. From those items, the Panel identified 13 separate domains of tinnitus distress

and selected 70 items most likely to be responsive to treatment effects. Eliminating redundant items while retaining good content validity and adding new items to achieve the recommended minimum of 3 to 4 items per domain yielded 43 items, which were then used for constructing TFI Prototype 1.Prototype 1 was tested at five clinics. The 326 participants included consecutive patients receiving tinnitus treatment who provided informed consent-constituting a convenience sample. Construct validity of Prototype 1 as an outcome measure was evaluated by measuring responsiveness of the overall scale and its individual items at 3 and 6 mo follow-up with 65 and 42 participants, respectively. Using a predetermined list of criteria, the 30 best-functioning items were selected for constructing TFI Prototype 2.Prototype 2 was tested at four clinics with 347 participants, including 155 and 86 who provided 3 and 6 mo follow-up data, respectively. Analyses were the same as for Prototype 1. Results were used to select the 25 best-functioning items for the final TFI.

Results: Both prototypes and the final TFI displayed strong measurement properties, with few missing data, high validity for scaling of tinnitus severity, and good reliability. All TFI versions exhibited the same eight factors characterizing tinnitus severity and negative impact. Responsiveness, evaluated by computing effect sizes for responses at follow-up, was satisfactory in all TFI versions. In the final TFI, Cronbach's alpha was 0.97 and test-retest reliability 0.78. Convergent validity (r = 0.86 with Tinnitus Handicap Inventory [THI]; r = 0.75 with Visual Analog Scale [VAS]) and discriminant validity (r = 0.56 with Beck Depression Inventory-Primary Care [BDI-PC]) were good. The final TFI was successful at detecting improvement from the initial clinic visit to 3 mo with moderate to large effect sizes and from initial to 6 mo with large effect sizes. Effect sizes for the TFI were generally larger than those obtained for the VAS and THI. After careful evaluation, a 13-point reduction was considered a preliminary criterion for meaningful reduction in TFI outcome scores.

Conclusions: The TFI should be useful in both clinical and research settings because of its responsiveness to treatment-related change, validity for scaling the overall severity of tinnitus, and comprehensive coverage of multiple domains of tinnitus severity.

The complete article is contained in Appendix L.

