A Type B or Type C tympanogram accompanied by hearing loss where there is a gap / difference between the air conduction and bone conduction thresholds on the audiogram at all or some frequencies is consistent with a conductive or mixed hearing loss.

Otoscopic Exam of the Ears

Otoscopy is a clinical procedure used to examine the structures of the ear, particularly the external auditory canal, tympanic membrane, and middle ear. Otoscopy is performed using a standard otoscope, a tool that shines a beam of light to help visualize and examine the condition of the ear canal and eardrum. The otoscopic exam is performed by gently pulling the auricle upward and backward to move the acoustic meatus in line with the canal.

The appearance of a normal healthy middle ear is as follows:

• Auditory canal: Some hair, often with yellow to brown cerumen.

- Ear drum:
 - Pinkish gray in color; shiny, translucent and in neutral position.
 - Intact; no bulging or retraction.
 - Malleus lies in oblique position behind the upper part of drum.

Observations from the otoscopic examination of the ear will be recorded, taking into consideration the following factors and any other of consideration:

- External auditory canal:
 - Hair (none, some, excessive)
 - Cerumen:
 - color (yellow, brown)
 - amount: minimal, normal ($\leq 50\%$); impacted (> 50%)
 - foreign body (yes/no)
 - Discharge or drainage (yes/no)
- Tympanic membrane
 - Color (pinkish-grey, red, white, yellow)
 - Translucency (transparent, opaque)
 - Position of the drum (retracted, neutral, or bulging)
 - Perforation / scars (yes/no)
 - Cone of light observed (yes/no)
- Position of the malleus handle: normal (behind the upper part of the drum); other

Subject Satisfaction with Study Outcome

The subject is asked to rate how satisfied he or she is with any change in his or her overall tinnitus following completion of the laser administration procedures with the Erchonia® THL[™] by using the 5-point Likert scale presented below to respond to the following question: "Overall, how satisfied or dissatisfied are you with any change in your tinnitus following the study procedures with the study laser device?"

- Very Satisfied
- Somewhat Satisfied
- Neither Satisfied nor Dissatisfied
- Not Very Satisfied
- Not at All Satisfied

BLINDING EFFICACY EVALUATION TOOLS

Subject Perceived Group Allocation and Rationale

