A fully-qualified enrolled subject will be provided by the study site, a device serial number, which translates to Group A or Group B based on the subject's group randomization. The subject and the site personnel will not be aware of any grouping at all. The devices will only be identified by serial number (see Randomization). The device will include a THL[™] Proper Use Reference Guide **(Appendix D).**

PROCEDURE ADMINISTRATION

- > The procedure administration phase extends over 4 consecutive weeks.
- ➤ The subject self-administers one procedure administration with the Erchonia® THL ™ (A or B) on each consecutive day of the 4-week procedure administration phase for a total of 28 self-administered procedures.
- Each procedure administration lasts 5 minutes each ear, for a total treatment time of 10 minutes.
- > Each procedure is self-administered by the subject in his or her own home.

PROCEDURE ADMINISTRATION PROTOCOL

The subject will need to follow the instructions in the Erchonia THL [™] Proper Use Reference Guide to correctly self-administer a procedure. These instructions read as follows:

1. Turn the THL [™] device on by pressing and holding the "Power Switch" for 3 seconds.

- 2. Ensure the green POWER ON indicator light is lit.
- 3. Put on the laser safety goggles provided.
- 4. Once the safety goggles are on, start the laser treatment by pressing the "START" icon on the treatment screen. Note: The protocol software is factory set and cannot be changed.
- 5. Ensure the laser indicator light is lit.
- 6. Hold the THL [™] laser light diode about 1 inch above your right ear and about 4 inches from your skin.
- 7. In a slow continuous sweeping motion, move the THL [™] down the right side of your neck.
- 8. Once you reach the bottom of your neck, in a slow continuous sweeping motion. move the THL ™ up your neck back to where you started, about 1 inch above your right ear, making sure to keep the laser about 4 inches away from the surface of your skin the whole time. This process is shown in the diagram below.

- 9. Continue this up and down sweeping motion on the right side for the whole 5 minutes of treatment.
- 10. Once the 5 minutes is done, the treatment will automatically stop. The "Time Remaining" display shows 0:00 and the laser lights and the laser indicator light will turn off.
- 11. Next, repeat steps 4 through10 for your left side (left ear and left side of neck) as shown in the diagram below.

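### The skin harms that the plan names are captured only by subject-initiated reports and an optional weekly contact, with no scheduled skin inspection and no recorded skin baseline

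*Combined protocol and SAP*

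**What the plan says.** **Named harms.** The ADVERSE EVENTS section says that adverse events are unlikely and not anticipated, then describes those that could feasibly occur as "not necessarily limited to skin irritation, discoloring, rash, indentations, and infection". It gives no body site.

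**Exposure.** Under PROCEDURE ADMINISTRATION PROTOCOL the subject starts about an inch above the ear: "In a slow continuous sweeping motion, move the THL [™] down the right side of your neck". The device then returns to its start, "making sure to keep the laser about 4 inches away from the surface of your skin the whole time", and the other side follows. Each side takes 5 minutes, once a day, for 28 sessions at home.

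**Scheduled examinations.** Baseline, the 4-week evaluation and the 2-week post-procedure endpoint each list audiometry, tympanometry and otoscopy. SAFETY ANALYSES tracks the same three: "changes in audiometric evaluations, including PTAs", "Changes in tympanogram type" and "Changes in otoscopic evaluation findings". The otoscopy section says that the examination concerns the structures of the ear, "particularly the external auditory canal, tympanic membrane, and middle ear". Its recorded items are for the canal, the eardrum and the malleus, with an open clause: "taking into consideration the following factors and any other of consideration".

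**Other routes.** Subjects are told to notify the investigator of any potential adverse event. Under WEEKLY ASSESSMENTS, site staff may telephone or e-mail once a week, partly to verify that no adverse event has happened. The treatment log is described as recording the days on which a treatment was given.

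**Analysis.** SAFETY ANALYSES compares observed or reported adverse events between groups, using a continuity-corrected chi-square on the percentage of subjects affected. The three ear tests are tracked in addition.

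**The concern.** The harms that the plan names are mostly skin findings, whereas the structured examinations look at hearing, middle-ear function, the canal and the eardrum. The scheduled measurements therefore do not look at the site where most of the named harms would appear.

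Two things follow. First, whether a mild rash or discoloration reaches the database depends on the subject choosing to report it, on a contact that staff are permitted but not required to make, or on someone noticing it by chance. Second, because skin status is not recorded at entry, a finding noticed later has no reference state: pre-existing discoloration and a new change would look the same.

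The device is intended for prescription home use. A short list of skin events is likely to be read as evidence that the skin tolerates repeated self-administration, and the data as planned would support that reading only weakly.

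**Working it through.** **1. Named harms against planned capture**

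| Harm named in ADVERSE EVENTS | Scheduled examination with a matching item | Baseline record | Other route |
|---|---|---|---|
| Skin irritation | None | None | Self-report; optional weekly contact; incidental observation |
| Discoloring | None for skin (the otoscopy colour items concern cerumen and the eardrum) | None for skin | Same |
| Rash | None | None | Same |
| Indentations | None | None | Same |
| Infection, outer-ear or neck skin | None | None beyond the open-wound exclusion | Same |
| Infection, ear canal | Otoscopy, discharge or drainage yes/no | Yes | Same |

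The only skin-related entries at enrolment are the exclusions in EXCLUSION CRITERIA PART 1 for open wounds and cancerous growths on or around the ears or neck. They screen subjects out; they do not record skin status in those who enter. The BASELINE VARIABLES list has no skin item, and the week-4 and endpoint assessment lists contain no adverse-event or skin item.

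**2. Illustration of what under-reporting does**

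The plan states no skin-event rate, no reporting rate and no power for the safety comparison, so there is no safety figure to reproduce. The one input taken from the plan is the group size in Sample Size Determination: 29 × 1/0.917 = 31.62, rounded to 32 per group. The rest is assumed:

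- p = true proportion of active subjects with a skin event
- c = share of those events that come to notice

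P(no recorded event among 32) = (1 − p·c)^32

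| p | c = 1 | c = 0.5 | c = 0.3 |
|---|---|---|---|
| 10% | 0.90^32 = 0.034 | 0.95^32 = 0.194 | 0.97^32 = 0.377 |
| 5% | 0.95^32 = 0.194 | 0.975^32 = 0.445 | 0.985^32 = 0.617 |

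**3. The planned between-group test**

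With 32 per group and no events on placebo, the continuity-corrected chi-square gives p = 0.062 for 5 active subjects with events and p = 0.032 for 6. At least 6 against 0 are therefore needed to reach 0.05.

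Power was obtained by summing binomial probabilities over all pairs of counts with p < 0.05, for assumed true rates of 20% active and 2% placebo and the same capture share in both groups:

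| Capture share | Effective rates | Power |
|---|---|---|
| 1 | 20% v 2% | 0.46 |
| 0.5 | 10% v 1% | 0.07 |
| 0.25 | 5% v 0.5% | 0.004 |

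Even with full capture the test is weak at this sample size; incomplete capture weakens it further. Blinding may keep capture similar in the two groups, but it does not recover events that are never recorded.

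**The case against.** The strongest reply is that the plan already has a route for these events. Subjects are told to report any potential adverse event, weekly contact is provided for, and observed as well as reported events count in the group comparison. The sham group is a concurrent reference for incidence even without a skin baseline. This stands, and it rules out two readings that a reader might infer:

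- **That the skin harms cannot be detected.** They can be reported, or noticed by chance, and would then be counted.
- **That the between-group safety comparison rests on the ear tests.** It rests on adverse events; the ear tests are tracked additionally.

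A reader might also infer that all the named harms lie on the skin of the ear and neck, or that the plan expects them. The documents support neither. The list gives no site and is open-ended, infection is not tied to skin, an ear-canal infection could show as discharge against a baseline, and the plan calls adverse events unlikely. The device is also held off the skin.

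It is also fair to say that the investigator handles the auricle during otoscopy, that the otoscopy form is open to other observations, and that the entry exclusions require some attention to the area. These allow incidental observation, but none requires a skin check or leaves a record when the skin is normal.

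The arithmetic illustrates under-reporting at assumed rates. It does not measure a known deficit, and nothing here bears on the primary efficacy result.

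Finally, the case report forms in Appendix N and the subject data capture forms are not in the text available, so a skin or adverse-event item there cannot be excluded. If one exists, the protocol and SAFETY ANALYSES do not refer to it.

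**Conclusion.** The point holds in a limited form. For skin irritation, discoloring, rash, indentations, and infection where it affects skin, capture depends on the subject's own report and an optional weekly contact. No scheduled examination includes the outer-ear and neck skin over which the device is swept, and no skin baseline is recorded. These events are therefore likely to be under-ascertained, and systematic comparison with baseline is not possible. They are not undetectable, and those reported do enter the planned comparison.

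The size depends on event and reporting rates that the documents do not give. For assumed true rates of 5% to 10% and capture of 30% to 100%, the chance of a zero count among 32 active subjects runs from 3% to 62%. A low or zero skin-event count would thus be weak evidence of skin safety. The conclusion assumes that the unseen forms add no structured skin item. The change is worth making because it improves capture of the plan's own named harms at little cost.

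**What to change.** 1. At baseline, week 4 and endpoint, add to the existing ear-examination form a yes/no item for each visible skin change named in ADVERSE EVENTS, covering both outer ears and both sides of the neck.
2. Add a daily yes/no column for any skin change to the treatment log that the subject already keeps. Visits at week 4 and two weeks later would miss transient events; the log column addresses these.
3. In SAFETY ANALYSES, add an item d: number and percentage of subjects with new or worsened skin findings relative to baseline, by group.
4. If Appendix N already contains such items, cite them in the protocol and in SAFETY ANALYSES instead of adding new ones.

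**Cost.** A few lines on a form, one log column, about a minute at visits where the ears are already examined, and one table. No extra visit, staff or equipment is needed. The downside is that trivial findings may be recorded and the reported adverse-event rate may rise slightly; the same collection in the sham group gives those findings a comparator.
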